**Table 37      Neonatal Infections**

Neonatal bacteraemia and sepsis (of early or late onset), meningitis, pneumonia and other respiratory infections such as bronchiolitis, caused by bacteria, parasites, viruses or fungi. Localised eye and ear infections, encephalitis, urinary tract infections and intestinal infections were excluded from these guidelines

Neonatal invasive blood stream infections: bacterial/fungal/viral	
Level	Description
1	Recognised pathogen identified using a validated method and from a normally sterile site.
2	Not meeting Level 1 of evidence AND Meeting 3 or more of the following criteria: • Temperature $\geq$ 37.5 °C or $<$ 35.5 °C • Tachycardia or new or more frequent episodes of bradycardia • New or more frequent episodes of apnea or increased oxygen requirement or increased requirement for ventilatory support • Lethargy or moving only when stimulated or hypotonia or irritability • Difficulty in feeding or abdominal distension • Pallor or poor perfusion or hypotension • Abnormal White Cell Count or I/T ratio $>$ 0.2 • Abnormal platelet count • Increased inflammatory markers (CRP, procalcitonin) • Metabolic acidosis as defined by a base excess

**CONFIDENTIAL**207636 (EPI-RSV-008 BOD)  
Protocol Amendment 4 Final

Neonatal invasive blood stream infections: bacterial/fungal/viral (continued)	
Level	Description
3	
Not meeting Level 1 or 2 of evidence AND
 
Meeting 2 or more of the following criteria:
 
 
• Temperature <math>\geq 37.5^{\circ}\text{C}</math> or <math>< 35.5^{\circ}\text{C}</math>
 
• Tachypnea or severe chest in drawing or grunting or cyanosis
 
• Change in level of activity
 
• History of feeding difficulty
 
• History of convulsions
 

Bacterial/fungal/viral meningitis	
Level	Description
1	Recognised pathogen identified using a validated method from cerebrospinal fluid (CSF)
2	
CSF pleocytosis OR positive IgM antibodies to a specific pathogen in the CSF AND
 
Recognised pathogen identified using a validated method from a normally sterile site (other than CSF) AND
 
Temperature <math>\geq 37.5^{\circ}\text{C}</math> or <math>< 35.5^{\circ}\text{C}</math> AND
 
1 or more criteria below:
 
 
• History of convulsions
 
• Lethargy or irritability
 
• Coma
 
• Apnea
 
• Bulging fontanel
 
• Neck stiffness
 

3a	
CSF pleocytosis AND
 
No pathogen identified using a validated method from a normally sterile site AND Temperature <math>\geq 37.5^{\circ}\text{C}</math> or <math>< 35.5^{\circ}\text{C}</math> AND
 
3 or more criteria below:
 
 
• History of convulsions
 
• Lethargy or irritability
 
• Coma
 
• Apnea
 
• Bulging fontanel
 
• Neck stiffness
 

3b	
No lumbar puncture done or no sample available AND
 
Temperature <math>\geq 37.5^{\circ}\text{C}</math> or <math>< 35.5^{\circ}\text{C}</math> AND
 
4 or more criteria below:
 
 
• History of convulsions
 
• Lethargy or irritability
 
• Coma
 
• Apnea
 
• Bulging fontanel
 
• Neck stiffness
 

**CONFIDENTIAL**207636 (EPI-RSV-008 BOD)  
Protocol Amendment 4 Final

Respiratory bacterial/fungal/viral infection	
Level	Description
1	
New or progressive or persistent infiltrate or shadowing or fluid in the intrapleural cavity or interlobar fissure on chest X-ray AND Recognised virus identified using a validated assay from an upper respiratory sample OR Recognised pathogen identified using a validated method and from a normally sterile site AND 3 or more criteria below:
 
 
• Temperature <math>\geq 37.5^{\circ}\text{C}</math> or <math>< 35.5^{\circ}\text{C}</math>
 
• Tachypnea or Nasal flaring or Chest in-drawing or Grunting
 
• Desaturations or increased oxygen requirements or increased ventilator requirements or oxygen saturation <math>< 95\%</math>
 
• Apneas
 
• Increased respiratory secretions or Increased suctioning requirements
 
• Cough or wheeze or crepitations
 
• Increased CRP or procalcitonin
 

2	
New or progressive or persistent infiltrate or shadowing or fluid in the intrapleural cavity or interlobar fissure on chest X-ray AND 4 or more criteria below:
 
 
• Temperature <math>\geq 37.5^{\circ}\text{C}</math> or <math>< 35.5^{\circ}\text{C}</math>
 
• Tachypnea or Nasal flaring or Chest in-drawing or Grunting
 
• Desaturations or increased oxygen requirements or increased ventilator requirements or oxygen saturation <math>< 95\%</math>
 
• Apneas
 
• Increased respiratory secretions or Increased suctioning requirements
 
• Cough or wheeze or crepitations
 
• Increased CRP or procalcitonin
 

3	
2 or more criteria below:
 
 
• Difficulty in breathing/Tachypnea
 
• Severe chest in-drawing
 
• Nasal flaring
 
• Grunting
 
• Wheezing
 
• Stridor
 
• Fever
 

Reference: Vergnano S, Buttery J, Cailes B, et al. Neonatal infections: Case definition and guidelines for data collection, analysis, and presentation of immunisation safety data. Vaccine. 2016;34 (49):6038-6046

**CONFIDENTIAL**207636 (EPI-RSV-008 BOD)  
Protocol Amendment 4 Final**Table 38      Respiratory Distress in the Neonate**

Constellation of clinical findings that support the presence of breathing difficulty in the neonate (0-28 days of life), independent from etiology or severity, and independent from the infant's gestational age or circumstances at the time of delivery

Level	Description
1	
Newborn 0 to 28 days of life
 
AND
 
Abnormal respiratory rate:
 
Measurement of number of breaths per minute consistent with:
 
 
- Tachypnea = respiratory rate of more than 60 breaths per minute
 
OR
 
- Bradypnea = respiratory rate of less than 30 breaths per minute
 
OR
 
- Apnea = cessation of respiratory effort (no breaths) for at least 20 seconds
 
 
AND
 
Clinical symptoms consistent with labored breathing:
 
 
- Nasal flaring (dilatation of alae nasi)
 
OR
 
- Noisy respirations in the form of expiratory grunting, stridor, or wheeze
 
OR
 
- Retractions or increased chest in-drawings on respiration (subcostal, intercostal, sternal, suprasternal notch)
 
OR
 
- Central cyanosis (whole body, including lips and tongue) on room air
 
OR
 
- Low Apgar Score (< 7 points) at 10 min, with respiration score <2
 
 
AND
 
Examination and documentation by qualified, trained, health care provider appropriate for the clinical setting.

2	
Newborn 0 to 28 days of life
 
AND
 
Abnormal respiratory rate:
 
Not measured, but reported as "rapid breathing", "slow breathing", having periods of "no breathing", or "abnormal breathing"
 
AND
 
Clinical symptoms consistent with labored breathing:
 
 
- Nasal flaring (dilatation of alae nasi)
 
OR
 
- Noisy respirations in the form of expiratory grunting, stridor, or wheeze
 
OR
 
- Retractions or increased chest in-drawings on respiration (subcostal, intercostal, sternal, suprasternal notch) or seesaw respirations
 
OR
 
- Central cyanosis (whole body, including lips and tongue) on room air
 
OR
 
- Low Apgar Score (< 7 points) at 10 min, with respiration score <2
 
 
AND
 
 
- No medical record documentation, but reporting through either a non-medical observer (e.g. mother, father, community worker) or via standard census mechanisms (e.g. Demographic and Health Surveillance System)
 
OR
 
- Collection of information from medical record review or billing codes.
 

3	No need for a level 3 per working group.
4	Not enough information to ascertain case of respiratory distress.
5	Not a case of respiratory distress in the neonate.

**CONFIDENTIAL**207636 (EPI-RSV-008 BOD)  
Protocol Amendment 4 Final

Reference: Leigh R. Sweet, Cheryl Keech, Nicola P. Klein, et al. Respiratory distress in the neonate: Case definition & guidelines for data collection, analysis, and presentation of maternal immunization safety data. *Vaccine*. 2017; 35: 6506-6517.

**Table 39 Preterm Birth**

Birth in less than 37 gestation-completed weeks (less than 259 days).

Prematurity and assessment of gestational age	
Level	Description
1	Certain last menstrual period date (LMP) LMP or intrauterine insemination (IUI) date or embryo transfer (ET) date with confirmatory 1st trimester scan ( $\leq 13 \frac{6}{7}$ weeks). OR 1st trimester scan ( $\leq 13 \frac{6}{7}$ weeks)
2a	Certain LMP* with 2nd trimester scan (14 $\frac{0}{7}$ weeks to 27 $\frac{6}{7}$ weeks). Note: If LMP and U/S do not correlate, default to U/S GA assessment. OR Certain LMP* with 1st trimester physical examination.
2b	Uncertain LMP with 2nd trimester scan (14 $\frac{0}{7}$ weeks to 27 $\frac{6}{7}$ weeks).
3a	Certain LMP with 3rd trimester scan $\geq 28 \frac{0}{7}$ weeks OR Certain LMP with confirmatory 2nd trimester Fundal Height (FH) OR Certain LMP with birth weight OR Uncertain LMP with 1st trimester physical examination.
3b	Uncertain LMP with FH. OR Uncertain LMP with newborn physical assessment. OR Uncertain LMP with Birth weight
*	Definitions of LMP, birth weight and physical assessment in referenced article.

Reference: Quinn JA, Munoz FM, Gonik B, et al. Preterm birth: Case definition & guidelines for data collection, analysis, and presentation of immunisation safety data. *Vaccine*. 2016;34(49):6047-6056.

**CONFIDENTIAL**207636 (EPI-RSV-008 BOD)  
Protocol Amendment 4 Final**Table 40 Failure to Thrive**

Failure to Thrive (FTT) can be broadly defined as a faltering of growth from a previously established pattern of growth. It is universally established that a diagnosis of failure to thrive should be based on anthropometric data. However no consensus exists as to which measurements achieve the highest specificity and sensitivity. Weight is generally regarded as the indicator of choice, particularly a change in growth velocity, and as such has been selected as the standard for this case definition with a weight for age deceleration as the primary indicator of failure to thrive. The case definition should be applied when there is no clear alternative diagnosis for the reported event to account for the combination of symptoms.

Level	Description
1	Infant age  determined by a documented birth date AND Weights obtained using an electronic scale AND At least 2 weights, measured at least 4 weeks apart AND Weight for age deceleration  through at least 2 centile spaces on growth chart 
2a	Infant age determined by a documented birth date AND Weights obtained using a beam balance scale AND At least 2 weights, measured at least 4 weeks apart AND Weight for age deceleration through at least 2 centile spaces on growth chart OR Infants with an undocumented birth date, where age is determined based on Mothers recall to nearest month AND Weights obtained using electronic scale AND At least 2 weights, measured at least 4 weeks apart AND Weight for age deceleration through at least 2 centile spaces on growth chart
2b	Infant age determined by a documented birth date AND Weights obtained using a spring balance scale AND At least 2 weights, measured at least 4 weeks apart AND Weight for age deceleration through at least 2 centile spaces on growth chart OR Weight measured using electronic scale or beam balance scale AND Length taken using Infantometer AND Weight for length less than or equal to the 3rd centile on the appropriate growth chart

**CONFIDENTIAL**207636 (EPI-RSV-008 BOD)  
Protocol Amendment 4 Final

Level	Description
3a	Infants with an undocumented birth date, where age is determined based on Mothers recall to nearest month AND Weight obtain using either beam balance or spring balance scale AND At least 2 weights, measured as least 4 weeks apart AND Weight for age deceleration through at least 2 centile spaces on growth chart
3b	Infants with no weight available AND Physical examination consistent with FTT  AND MUAC  indicative of severe wasting

This case definition is limited to infants up to 12 months of age.Weight should be documented on the appropriate growth chart at the time of assessment. A fall through 2 centile spaces may be demonstrated at any point in the first 12 months of life, using any two weights as long as they are taken at least 4 weeks apart. Details of use of the weight balances allowable under this case definition and use of the Infantometer for length assessment are presented in the reference given below.For infants born at 37 weeks gestation or above, the WHO growth charts should be applied. When using weight for age use the growth chart most accurate for the infants age. The birth to 6 months age range should be used where data is available for this range only, the birth to 2 years chart should be used where data is available beyond 6 months of life. When using weight for length, use the chart for birth to 2 years. For infants born less than 37 completed weeks gestation, the Intergrowth charts for postnatal growth standards in preterm infant should be used. All infants should be plotted on their respective growth chart using their corrected age. Links to relevant growth charts are presented in the reference given below.Physical examination with signs of Failure to Thrive (must include at least 2 findings, with at least one major finding)  
Major findings: Reduced subcutaneous fat stores; poor muscle mass; loose skin folds; prominent ribs; thin limbs  
Other less specific signs include: sparse hair; rashes; pallor; miserable; lethargy/fatigue.Mid Upper Arm Circumference (MUAC): For infants 0–6 months, a MUAC of 6 110 mm is indicative of severe wasting. For infants 6–12 months, a MUAC of 6 115 mm is indicative of severe wasting. Instructions on performing MUAC are presented in the reference given below.

Reference: Ross E, Munoz F, Edem B et al. Failure to thrive: case definition and guidelines for data collection, analysis, and presentation of maternal immunization safety data. Vaccine. 2017; 35:6483-6491.

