Review infant diary card		0	0	0		0
Collect infant diary card e f		0	0	0		0
Transcribe applicable infant diary card data to eCRF		●	●	●		●
Weight, length, head circumference, results of targeted medical history, and results of physical examination	●	●	●	●		
Record prescription medications / vaccinations	●	●	●	●	●	●
Record neonatal events of interest	●	●	●	●		
Clinical evaluation of potential LRTI						●
Nasal swab b						● c
Record all hospitalizations and clinically significant events h	●	●	●	●	●	●
Record SAEs related to study participation	●	●	●	●	●	●
Study conclusion				●		
Investigator sign-off on eCRF before analysis		●	● g	●		

**LAR** = legally acceptable representative; **LRTI** = lower respiratory tract illness; **NB** = newborn; **RTI** = respiratory tract illness; **SAE** = serious adverse event; **M=month**; **Y** = year. Grey shaded columns represent study procedures to be performed for active/passive surveillance of RTIs/LRTIs which are applicable throughout the entire study period (from birth up to study end). **Note:** The double-line borders indicate primary analyses.

● is used to indicate a study procedure that requires documentation in the individual electronic case report form (eCRF).

○ is used to indicate a study procedure that does not require documentation in the individual eCRF.

**CONFIDENTIAL**207636 (EPI-RSV-008 BOD)  
Protocol Amendment 4 Final

- a If local regulations require that written consent / confirmation of consent for the infant's participation be obtained at birth.
- b Visits 2-, 3-, and 4-NB and LRTI assessment visits may take place in the subject's home (if the standard of care allows for home visits), at the investigator's clinical facility or at another facility per the investigator's judgment.
- c If more than one assessment visit is conducted to evaluate a potential LRTI, additional nasal swabs may be collected at the discretion of the Investigator.
- d Distribute at V1-NB: Distribute additional diary cards at subsequent visits as needed.
- e Collect diary cards that are fully filled out and / or document (L)RTI symptoms that have ended. Provide new diary cards as needed.
- f Collect all diary cards for potential RTIs that are considered resolved. Collect the diary card for the current potential LRTI once the LRTI symptoms have ended.

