##### 11.1.1.2. Pregnancy related events of interest from Visit 1 through Visit 6.

Although pregnancy related events of interest occur within the first 42 days after delivery they may only be detected later, and are to be reported throughout the study. They are listed below. Of note, some events of interest fall under a single category but have multiple subcategories. For example, hypertensive disorders of pregnancy is an event with three subcategories that include: 1) gestational hypertension; 2) pre-eclampsia; and 3) pre-eclampsia with severe features (including eclampsia). For each event, the investigator should select the event and the applicable sub-category.

**CONFIDENTIAL**207636 (EPI-RSV-008 BOD)  
Protocol Amendment 4 Final

- Maternal death
- Hypertensive disorders of pregnancy:
  - Gestational hypertension,
  - Pre-eclampsia,
  - Pre-eclampsia with severe features (including eclampsia)
- Antenatal bleeding:
  - Morbidly adherent placenta
  - Placental abruption
  - Cesarean Scar Pregnancy
  - Uterine rupture
- Postpartum hemorrhage
- Fetal growth restriction
- Dysfunctional labor
  - first stage of labor
  - second stage of labor
- Gestational diabetes mellitus,
- Non reassuring fetal status
- Pathways to preterm birth:
  - Premature preterm rupture of membranes,
  - Preterm labor,
  - Provider-initiated preterm birth.
- Chorioamnionitis
- Oligohydramnios
- Polyhydramnios
- Gestational Liver Disease:
  - Intrahepatic Cholestasis of Pregnancy (ICP)
  - Acute Fatty Liver of Pregnancy
- Maternal Sepsis
- Any other pregnancy related event considered by the investigator to be of concern (specify)

For events of interest that include subcategories, the frequency of the main event of interest and of each event subcategory will be included in the analysis. The overall frequency will include mothers who present with at least one of the subcategory events.

**CONFIDENTIAL**207636 (EPI-RSV-008 BOD)  
Protocol Amendment 4 Final**11.1.1.3. Neonatal events of interest from birth through 28 days of age**

Neonatal events of interest occur within the first 28 days after birth, but may only be detected later and are to be reported throughout the study. They include:

- Small for gestational age,
- Low birth weight including very low birth weight,
- Neonatal encephalopathy,
- Congenital microcephaly,
  - Postnatally diagnosed
  - Prenatally diagnosed
- Congenital anomalies,
  - Major external structural defects
  - Internal structural defects

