  - Functional defects
- Neonatal death,
  - Neonatal death in a preterm live birth (gestational age $\geq$ 28 to < 37 weeks)
  - Neonatal death in a term live birth
- Neonatal infections,
  - Blood stream infections
  - Meningitis
  - Respiratory infection
- Respiratory distress in the neonate,
- Preterm birth,
- Failure to thrive,
- Large for gestational age,
- Macrosomia,
- Any other neonatal event considered by the investigator to be of concern (specify, e.g. neurodevelopment delay)

For events of interest that include subcategories, the frequency of the main event of interest and of each event subcategory will be included in the analysis. The overall frequency will include infants who present at least one of the subcategory events.

**CONFIDENTIAL**207636 (EPI-RSV-008 BOD)  
Protocol Amendment 4 Final**11.1.2. Secondary endpoints**

- Pregnancy related events of interest from Visit 1 through Visit 6 (as defined in primary endpoints) for each GAIA level of diagnostic certainty (where applicable and feasible).
- Neonatal events of interest from birth through 28 days of age (as defined in primary endpoints) for each GAIA level of diagnostic certainty (where applicable and feasible).

Of note, some events of interest fall under a single category but have multiple subcategories. For each event, the investigator should identify the event and select the applicable sub-category and the GAIA level of diagnostic certainty.

- RSV-A neutralizing antibody titers in maternal blood at delivery
- RSV-A neutralizing antibody titers in cord blood at delivery.
- Episode(s) of RSV-LRTI from birth up to 1 year of age.
- Episode(s) of RSV hospitalization from birth up to 1 year of age.

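### Failure to thrive is a primary event confined to the first 28 days, but Table 40 defines it over 12 months and no scheduled pair of weights closes by day 28

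*Protocol*

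**What the plan says.** Section 11.1.1.3 of the protocol is headed "Neonatal events of interest from birth through 28 days of age" and includes "Failure to thrive" among twelve named events. It adds that neonatal events occur within 28 days but may be detected, and are to be reported, later. A footnote to Figure 1 (Section 4) makes the 0-28 day limit part of the definition of these events.

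Appendix D, Table 40 takes weight-for-age deceleration as the primary indicator of failure to thrive:

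- Levels 1, 2a, 3a and the first branch of Level 2b all require "At least 2 weights, measured at least 4 weeks apart", with a fall through at least two centile spaces.
- Footnote 1 limits the definition to infants up to 12 months of age. Footnote 2 states: "A fall through 2 centile spaces may be demonstrated at any point in the first 12 months of life".
- The second branch of Level 2b needs no pair. It requires "Weight for length less than or equal to the 3rd centile on the appropriate growth chart", with a named type of scale and an infantometer.
- Level 3b is for "Infants with no weight available" and rests on examination and mid-upper-arm circumference.

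Table 6 (Section 8.3) schedules "Weight, length, head circumference, results of targeted medical history, and results of physical examination" at the four newborn visits only, and has neonatal events recorded at all four. Table 7 (Section 8.4) sets the visit windows. Section 11.11 places the analysis of neonatal events at the point when data up to 42 days post-delivery are available.

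**The concern.** Two rules fixed in the protocol pull against each other. The endpoint belongs to a 28-day window, while the case definition describes a process that may be shown at any time in a year and whose main criterion itself takes at least 28 days to observe. Most other neonatal events on the list can be placed at birth or at a dated clinical event. A fall across centiles happens somewhere between two weighings.

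The study exists to supply background rates for interpreting safety data in later maternal vaccine trials (Sections 1.1 and 1.2). A rate that is low because the definition could hardly register a case by day 28 would be read as rarity. A rate that includes later faltering would be read as a neonatal rate when it is not. Because neonatal events are recorded at all four newborn visits, the looser reading could also give different figures in the day-42 report and the final report.

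**Working it through.** **Inputs.** Endpoint window: day 0 to day 28 (Section 11.1.1.3). Minimum spacing: 4 weeks = 28 days (Table 40). Weight visits (Tables 6 and 7): Visit 1-NB, days 0-21; Visit 2-NB, days 35-49; Visit 3-NB, days 166-194; Visit 4-NB, days 351-379. No figure is stated in the plan for this event, so there is none to reproduce.

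**Step 1: does any scheduled pair close by day 28?** Smallest gap = start of the later window minus end of the earlier one. Largest gap = end of the later window minus start of the earlier one. A pair closes, at the earliest, at the start of the later window.

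| Pair | Gap in days | Earliest close | By day 28? |
|---|---|---|---|
| 1-NB and 2-NB | 14 to 49 | day 35 | no |
| 1-NB and 3-NB | 145 to 194 | day 166 | no |
| 1-NB and 4-NB | 330 to 379 | day 351 | no |
| 2-NB and 3-NB | 117 to 159 | day 166 | no |
| 2-NB and 4-NB | 302 to 344 | day 351 | no |
| 3-NB and 4-NB | 157 to 213 | day 351 | no |

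**Step 2: could any pair of weights fit?** Among whole days 0 to 28, the only pair at least 28 days apart is day 0 with day 28. There is no day-28 visit, so this needs a chance weight from the medical records.

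**Step 3: is the spacing rule itself attainable later?** For Visit 1-NB with Visit 2-NB, spacing is met if Visit 1-NB is no later than (Visit 2-NB day minus 28): day 7 for a day-35 visit, day 14 for day 42, day 21 for day 49. There are 22 x 15 = 330 whole-day combinations, of which 8 + 9 + ... + 22 = 225 qualify (225/330 = 68%; a count of combinations, not a probability). A recorded birth weight with Visit 2-NB gives 35 to 49 days, so it always qualifies.

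**Step 4: how much of such a pair lies outside the window?** For birth weight to Visit 2-NB, the share after day 28 is (Visit 2-NB day minus 28) / Visit 2-NB day:

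- day 35: 7/35 = 20%
- day 42: 14/42 = 33%
- day 49: 21/49 = 43%

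A pair starting at Visit 2-NB or later lies wholly outside.

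**Step 5: the remaining routes.** The weight-for-length branch of Level 2b can be met on a single examination at Visit 1-NB. Level 3b needs an infant with no weight, although weight is scheduled at every newborn visit, and an arm circumference, which Table 6 does not schedule.

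**The case against.** The strongest reply is the late-detection clause. Neonatal events may be found and reported after day 28, all four newborn visits record them, and the first analysis waits for day-42 data. On this view, a fall shown by birth weight and Visit 2-NB meets Table 40 and is simply detected late, and any rule for assigning it to the window is a derivation detail for the SAP.

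Part of this stands. The spacing rule can be met after day 28, so a reader might infer that the criterion can never be satisfied, or that a Visit 1-NB on day 21 defeats it. The documents do not support either. Small for gestational age and low birth weight (Tables 31 and 32) already call for a weight within 24 or 48 hours of birth, and that weight paired with Visit 2-NB is always far enough apart. A reader might also infer a structural zero, for example 0 of 270 reported as 0% with the Table 17 limits of 0 to 1.4%. That is too strong as well, since weight-for-length cases, Level 3b cases and record weights on days 0 and 28 remain possible (Section 8.6.4 has neonatal records reviewed). Nor does any section give sites a choice of reading.

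What does not stand is the claim that late detection resolves the conflict. The clause covers an event that occurred by day 28 and was noticed later. Weights on days 0 and 42 cannot show on which side of day 28 the fall took place. The window and the case definition are both fixed in the protocol and disagree, so this is more than detail deferred to the SAP.

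**Conclusion.** The point holds as a conflict between the 28-day window and Table 40. It does not show that the endpoint is unattainable. Followed strictly, the main criterion cannot be met from scheduled weights within the window, and the frequency is near zero apart from the narrow routes above. Followed loosely, the frequency counts faltering after day 28: 20% to 43% of the interval between birth and Visit 2-NB lies beyond the window, and all of any pair starting at Visit 2-NB or later does.

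The size in cases cannot be given, because the documents state no rate for failure to thrive. The conclusion assumes visits within the Table 7 allowed intervals (its footnote lets out-of-window visits be analysed, but Visit 2-NB would have to be at least 7 days early to matter) and no routine day-28 weight. It affects one of the twelve named neonatal events, so it should be corrected, but it does not undermine the primary objective as a whole.

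**What to change.** Reconcile the window with Table 40:

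- Remove failure to thrive from the 28-day list in Section 11.1.1.3, the synopsis and the matching secondary endpoint by GAIA level.
- Report it as an infant event from birth through 12 months at the final analysis. Apply Table 40 to the recorded birth weight and the Visit 1-NB to 4-NB weights and lengths, with the growth charts that its footnotes name.
- Keep the investigator's judgement that no other diagnosis clearly explains the picture. Table 40 requires it, and a derivation from weights alone would drop it.
- Give the GAIA level where the type of scale is recorded; Table 6 does not show that it always is.
- If an early figure is wanted at the day-42 analysis, label it as failure to thrive shown by Visit 2-NB, not by day 28.

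The cost is a change of endpoint wording and one derivation. No visits or measurements are added. The drawback is that the full result moves from the day-42 statistical report to the final report.
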